## Clinical Protocol FIH-3

Doc No: CLINP1837  
Revision: D  
DCO No: 25-009  
Effective Date: 02/06/25

attached to the Inflow Access Port via a quick-connect (“Screw Lock”) fitting. The Distal Outflow Catheter tip is inserted into a vein in the upper extremity, with a taper to facilitate easy vein insertion. The Distal Outflow Catheter is joined to the Proximal Outflow Catheter using a connector (“Inline Connector”) and Screw Lock fittings. The proximal end of the Proximal Outflow Catheter can be trimmed to the appropriate length and attached to the Outflow Access Port via a Screw Lock fitting. During placement of the Amplifi System, the Pump is connected to the Controller via the integrated Pump cable. A control algorithm in the Controller automatically increases the speed of the Pump to maintain an elevated WSS in the cephalic vein as the treatment progresses and the cephalic vein dilates. During placement of the Amplifi System, the Blood Flow Sensor is connected to the Pump via the integrated Blood Flow Sensor cable.

Additional details of the Amplifi System can be found in the Investigator’s Brochure.

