#### Safety Measures

- **Rate of Occurrence of Major Device-Related Adverse Events (MDRAE)\* defined as:** [Timeframe: from device implantation and up to 30 days from device removal and AVF creation]
  - Amplifi System-related death;
  - Amplifi System-related major bleeding, major pneumothorax, major air

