## **8.4 Laboratory Assessments**

- A routine chemistry panel will be evaluated at baseline, at day 1 prior to Amplifi System placement, and at the end of Amplifi System treatment.
- A complete blood count (CBC) will be evaluated at baseline, on day 1 prior to Amplifi System placement, daily during the Amplifi System treatment period, at the end of Amplifi System treatment after Amplifi System removal, and 1, 2 weeks and 6 weeks after Study AVF creation. The baseline CBC results will be used to assess eligibility, the daily testing during the Amplifi System treatment period and the testing 1, 2 weeks and 6 weeks after Study AVF creation will be used to assess for hemolysis and anemia.
- PFH and LDH will be evaluated at baseline, on day 1 prior to Amplifi System placement, daily during the Amplifi System treatment period, at the end of Amplifi System treatment period after Amplifi System removal, and 1, 2 weeks and 6 weeks after Study AVF creation to assess for hemolysis.
- ACT will be evaluated during Amplifi System placement and removal, as per the Amplifi IFU, and during AVF creation, as per Standard of Care.

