## Clinical Protocol

### FIH-3

Doc No: CLINP1837  
Revision: D  
DCO No: 25-009  
Effective Date: 02/06/25

system during the placement, operation, use, or removal of the Amplifi System that is not due to a cause other than the placement, operation, use, or removal of the Amplifi System; wherein the air embolism is documented by imaging and:

- results in air embolism-related hypotension, arrhythmia, hemodynamic instability, paradoxical embolization, myocardial infarction, stroke, mesenteric ischemia, or death;
- requires a procedure or surgery to remove the air that forms after air embolism; or
- requires a thrombectomy procedure or surgery, thrombolytic therapy, or long-term anticoagulation to remove thrombus that forms after air embolism.
- *Amplifi System-related major thrombosis* is defined as the formation of thrombus in an artery, vein, or the right atrium due to the placement, operation, use, or removal of the Amplifi System, wherein the thrombosis is documented by imaging and the Subject requires a thrombectomy procedure or surgery, thrombolytic therapy, or long-term anticoagulation; not inclusive of a thrombectomy procedure or surgery that occurs during the creation of the Subject AVF.
- *Amplifi System-related major thromboembolism* is defined as thromboembolism in the arterial or venous system due to the placement, operation, use, or removal of the Amplifi System, wherein the thromboembolism is documented by imaging and the Subject requires a thrombectomy procedure or surgery, thrombolytic therapy, or long-term anticoagulation; not inclusive of a thrombectomy procedure or surgery that occurs during the creation of the Subject AVF.
- *Amplifi System-related major hemolysis* is defined as hemolysis documented by laboratory testing during the Amplifi System treatment period that is not due to a cause other than the placement, operation, use, or removal of the Amplifi System, and requires blood transfusion and/or results in thrombotic events, multiple organ failure and mortality.
- *Amplifi System-related major thrombocytopenia* is defined as a platelet level of  $\leq 51,000$  per microliter during the Amplifi System treatment period that is not due to a cause other than the placement, operation, use, and removal of the Amplifi System, and requires transfusion.

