## Clinical Protocol

### FIH-3

Doc No: CLINP1837  
Revision: D  
DCO No: 25-009  
Effective Date: 02/06/25

Amplifi System-related complication and the loss or damage to sites for dialysis access or the need to convert an AV fistula to an AV graft or hemodialysis catheter; not inclusive of the placement of pressure dressings, the placement or removal of skin sutures, the creation of an AVF or AVG, or the placement or removal of a hemodialysis catheter.

- *Amplifi System-related complication* is defined as any untoward medical occurrence, unintended disease or injury, or untoward clinical sign or abnormal lab finding related to the placement, use, operation, or removal of the Amplifi System; not inclusive of mild-moderate hand, wrist, arm, neck, or face swelling that resolves within 7 days after the end of the Amplifi System treatment period.
- *Amplifi System treatment period* is defined as starting when a needle is used to access the internal jugular vein or cephalic vein at the start of Amplifi System placement and ending when the Inflow Catheter and Distal Outflow Catheter have been completely removed and any related incisions have been closed.
- *Aneurysm of Study AVF* is defined as expansion of the intimal, medial, and adventitial layers of the wall of a segment of outflow vein of a Study AVF in the region between the Study AVF anastomosis and the axilla that requires treatment through an interventional procedure or surgery.
- *Anti-platelet agent* is defined as a pharmaceutical that is approved for use to decrease platelet aggregation and inhibit thrombus formation.
- *AVF circuit* is defined as the region starting with the origin of the inflow artery and continuing to the junction of the superior or inferior vena cava and the right atrium.
- *AVF creation* is defined as the making of an opening between the lumen an artery and vein for the purpose of creating a vascular access for hemodialysis, inclusive of interventional and surgical methods.

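### Major hemolysis and major thrombocytopenia need a laboratory finding within the treatment period, although the composite runs to 30 days and blood is scheduled after removal, so the major-event rate can be understated

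*Protocol*

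**What the plan says.** The main safety measure, in the Synopsis and in Section 4.5, is the rate of major device-related adverse events. It is counted "from device implantation and up to 30 days from device removal and AVF creation". Major hemolysis and major thrombocytopenia are listed components.

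Appendix 1 gives the operative definitions.

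- **Major hemolysis** is "hemolysis documented by laboratory testing during the Amplifi System treatment period", attributable to the device, that needs blood transfusion and/or leads to thrombotic events, multiple organ failure and mortality.
- **Major thrombocytopenia** is a platelet level at or below 51,000 "per microliter during the Amplifi System treatment period that is not due to a cause other than" the device's placement, operation, use and removal, and that needs transfusion.
- **The treatment period** is a defined term. It starts at first needle access, "ending when the Inflow Catheter and Distal Outflow Catheter have been completely removed and any related incisions have been closed".

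Section 8.4 sets the blood draws. CBC, PFH and LDH are taken daily during treatment. A separate end-of-treatment CBC is taken "at the end of Amplifi System treatment after Amplifi System removal". PFH and LDH are taken "at the end of Amplifi System treatment period after Amplifi System removal, and 1, 2 weeks and 6 weeks after Study AVF creation". The stated purpose of PFH and LDH is to assess for hemolysis; the stated purpose of the follow-up CBC is to assess for hemolysis and anemia. Table 4 allows ±7 days for laboratory tests after AVF creation.

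**The concern.** The outcome window and the definitions of two of its components do not match. The composite stays open for 30 days after removal, but the laboratory finding that triggers either component has to fall in a period that closes when removal is finished and the wound is shut. The protocol nevertheless collects the relevant tests after that point and, for hemolysis, says that they are taken to look for it.

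Both definitions also list removal among the device causes, yet the window for the finding shuts as removal is completed. No scheduled draw is fixed between catheter removal and incision closure.

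At stake is the statement that the study is meant to support, namely that major events are in an acceptable range (Sections 1.0 and 4.1). A rule that can drop a device-related event and can never add one biases that rate downward.

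**Working it through.** The protocol gives no figure to reproduce: Section 14.1 says the study is not powered for a specific outcome. The check sets the definitions against the sampling schedule by date.

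**Inputs.** Treatment period: ends at catheter removal and incision closure (Appendix 1). Outcome window: 30 days after removal and AVF creation (Section 4.5). Laboratory visits: end of treatment, then weeks 1, 2 and 6 after AVF creation (Section 8.4), each ±7 days (Table 4). AVF creation immediately follows removal (Section 4.3), so day 0 serves for both.

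**Dates.** Visit range = 7 × week ± 7 days.

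| Sample | Days after removal | Inside 30-day outcome? | Can trigger either definition? |
|---|---|---|---|
| Daily, during treatment | before removal | yes | yes |
| End of treatment | about 0 | yes | only if drawn before incision closure |
| Week 1 | 7 ± 7 = 0 to 14 | yes | no |
| Week 2 | 14 ± 7 = 7 to 21 | yes | no |
| Week 6 | 42 ± 7 = 35 to 49 | no | no |

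Three of the four post-removal time points lie inside the outcome window. Of these, weeks 1 and 2 cannot trigger either component on the natural reading, and the end-of-treatment sample can do so only if it happens to precede incision closure. Section 8.4 does not fix its timing against closure. Week 6 lies outside the 30-day window, so nothing is lost there.

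**What the time limit covers.** In both definitions it attaches to the laboratory finding. The qualifying consequences (transfusion and, for hemolysis, thrombotic events, organ failure and mortality) carry no such limit. Hemolysis documented on a treatment day and transfused some days after removal still counts.

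**Other routes into the composite.** Related re-hospitalization and prolonged hospitalization are components in their own right with no treatment-period limit. A later thrombotic event could qualify as major thrombosis. The last component is a judgement by two parties, and the text differs on who they are: the Investigator and the Medical Monitor in Section 4.5, the Investigator and the CEC in Appendix 1. A subject transfused without a longer or repeat admission, and without another listed event, therefore reaches the composite only by that judgement.

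**Size.** With the full 10 subjects, one event missed in this way changes the rate by 1/10 = 10 percentage points.

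**The case against.** Much can be said for the protocol, and part of it stands.

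- **The hemolysis wording is ambiguous.** The time limit may qualify the hemolysis and not the test. On that reading, a sample just after removal can document hemolysis that occurred during treatment. This is possible but less natural, and it does not help thrombocytopenia, where the platelet value itself is tied to the period.
- **The period ends at incision closure, not at removal.** A reader might infer that no post-removal sample can ever count. The text does not support that: a draw between removal and closure counts.
- **Only the laboratory trigger is limited.** A reader might infer that all 30 days after removal are closed to these two components. They are not, because later consequences of a finding made during treatment still qualify.
- **Daily draws are required.** A reader might use the 12-hour daily window in Table 4 to argue that a large share of treatment time has no countable sample. Section 8.4 requires daily draws during treatment as well as the end-of-treatment sample. The argument works only if a draw required during treatment is moved to after removal.
- **Pump speed.** Section 2.2 says the controller "automatically increases the speed of the Pump to maintain an elevated WSS in the cephalic vein", so a reader might want the last sample drawn before the Pump stops. The documents do not make this necessary. Once the definitions are aligned, the post-removal sample counts, and replacing it would lose the immediate PFH and LDH that could show removal-related hemolysis.
- **Exposure limits are not unusual in this appendix.** Pneumothorax and air embolism are also tied to placement, operation, use or removal. Bleeding, thrombosis and thromboembolism have no treatment-period limit, however, and hemolysis is the one for which post-removal tests are expressly scheduled.
- **Late events stay visible.** Adverse events are tabulated by type, severity and relation (Section 14.2.3). That is true, but the named safety outcome is the major-event rate.

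The stated purpose of the follow-up CBC does not mention platelets, so the conflict with the protocol's own purpose is strongest for hemolysis.

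**Conclusion.** The mismatch is real and narrow. A device-related hemolysis or platelet fall first documented at week 1 or 2, or on an end-of-treatment sample drawn after incision closure, does not meet its own definition even if the subject is transfused. Such a case reaches the major-event rate only through another component or by discretion, so the rate can be understated; each such event is worth 10 percentage points at n=10.

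For hemolysis this rests on reading the time limit as applying to the test. It also needs a case that first shows after removal, has a qualifying consequence and is not caught elsewhere. The documents give no frequency for such cases, so the expected bias cannot be estimated, only its direction and its size per event. The study is small and descriptive, with no numerical limit for an acceptable range. This should be fixed before events are adjudicated, but it does not invalidate the design.

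**What to change.** In Appendix 1, in the definitions of major hemolysis and major thrombocytopenia, replace the treatment-period limit with a window *from device implantation through 30 days after device removal*, matching Section 4.5. Keep the device-causality requirement and the transfusion or other consequence requirements as they are.

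Keep the existing post-removal CBC, PFH and LDH in Section 8.4. They then count towards the outcome, and no draw needs to be moved or added. The instruction in Section 7.2 on a major hemolysis event is limited to the treatment period by its own wording and is not affected.

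The cost is two wording changes by amendment. The reported major-event rate may be slightly less favourable. The change should precede adjudication, since redefining a safety outcome once events are known would be hard to defend.

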### 7.2 Amplifi System Treatment

Prior to treating Subjects with the Amplifi System, Investigators will review the Amplifi System IFU and Protocol, and will refer to the Amplifi System IFU, Operator's Manual and Protocol during treatment, as needed.

If, during the Amplifi System treatment period, a Subject has an *Amplifi System-related major hemolysis event*, the Investigator will discontinue Amplifi System treatment, provide treatment for the hemolysis, and create an AVF with the treated cephalic vein as soon as possible, if clinically indicated. Subject(s) will continue their post AVF follow-up, if applicable.

If, during Amplifi System treatment period, a Subject has experienced pump early stoppage, malfunction or deficiencies prior to the scheduled end of treatment, please refer to **Section 7.5 Pump Malfunction and Stoppage**.

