## Appendix 1: Definitions

- *Abandonment of Study AVF* is defined as the discontinuation of the clinical use of Study AVF because it is no longer functional and considered not to be salvageable, including the discontinuation of the clinical use of Study AVF because it can no longer be used for prescribed hemodialysis, because it is unable to provide adequate blood flow, or because it is deemed unsafe for the patient, and the associated problem(s) cannot be corrected by any medical, procedural, or surgical intervention.
- *Amplifi System and AVF local infection* is defined as: 1) the presence of purulent discharge from the Inflow Catheter skin exit site, the Distal Outflow Catheter skin exit site, or the Study AVF skin incision; or 2) the presence of serous discharge from the Inflow Catheter skin exit site, the Distal Outflow Catheter skin exit site, or the Study AVF skin incision with erythema, induration, or tenderness and a positive culture of the serous discharge.
- *Amplifi System component replacement* is defined as the replacement of one or more components of the Amplifi System during the Amplifi System treatment period, not including replacement or addition of Access Port caps, suture anchoring tools, a Patient Vest, or Patient Vest components.
- *Amplifi System-related major complication* is defined as:
  - Amplifi System-related death;
  - Amplifi System-related major bleeding, major pneumothorax, major air embolism, major thrombosis, major thromboembolism, major hemolysis, or major thrombocytopenia; local infection
  - Amplifi System-related re-hospitalization or prolonged hospitalization;
  - Amplifi System-related major surgery or major interventional procedure; or
  - any Amplifi System-related complication determined to be an Amplifi System-related major complication by both an Investigator and the CEC.
- *Amplifi System-related major bleeding* is defined as:
  - overt bleeding plus a drop in hemoglobin of 3 to 5 g/dL wherein the hemoglobin drop is related to the bleeding;
  - transfusion for overt bleeding;
  - bleeding requiring an interventional procedure or surgery for control (not including the placement or removal of skin sutures or pressure dressings);
  - the administration of intravenous vasoactive agents for overt bleeding; or
  - probable or definite fatal bleeding.

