## Clinical Protocol

### FIH-3

Doc No: CLINP1837  
Revision: D  
DCO No: 25-009  
Effective Date: 02/06/25

creation site.

- *Internal jugular vein suitable for Amplifi Inflow Catheter insertion* is defined as a widely patent internal jugular vein without thrombus and with a lumen diameter  $\geq 8.5$  mm (during Valsalva) that does not contain any catheter or intravascular implant and is deemed to be suitable for Inflow Catheter insertion by the Investigator.
- *Intervention-free AVF maturation* is defined as AVF maturation (as defined above) in the absence of any interventional procedure, surgery, or medical treatment to promote maturation of the AVF.
- *Interventional procedure, surgery, or medical treatment to promote maturation of the AVF of Study AVF* is defined as an interventional procedure, surgery, or a medical treatment intended to:
  - increase the diameter of a segment of an artery or vein in Study AVF circuit or increase Study AVF blood flow, including by angioplasty or stent placement, cutting, removing, or otherwise rendering a venous valve incompetent, resecting of a segment of outflow vein, and surgical revision of the Study AVF anastomosis;
  - remove thrombus from the lumen of the artery or vein in Study AVF circuit; and
  - reduce the flow of blood in Study AVF tributaries including by embolization or surgical ligation;and excluding planned superficialization of a segment of Study AVF outflow vein for the purpose of enabling easier cannulation.
- *Interventional procedure, surgery, or medical treatment to achieve or maintain functional patency of Study AVF* is defined as an interventional procedure, surgery, or a medical treatment intended to:
  - increase the diameter of a segment of artery or vein in Study AVF circuit or increase Study AVF blood flow, including by angioplasty or stent placement;
  - cut, remove, or otherwise render a venous valve incompetent;
  - surgically revise the Study AVF anastomosis;
  - remove thrombus from the lumen of the artery or vein in Study AVF circuit;
  - resect a segment of Study AVF outflow vein; and
  - reduce the flow of blood in Study AVF tributaries including by embolization or surgical ligation;inclusive of interventional procedures, surgeries, and medical treatments intended to promote maturation of Study AVF; and  
exclusive of planned superficialization of a segment of Study AVF outflow vein for the purpose of enabling easier cannulation.

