## Clinical Protocol FIH-3

Doc No: CLINP1837  
Revision: D  
DCO No: 25-009  
Effective Date: 02/06/25

Publication	Overview	Safety Data
		
bleeding. In contrast, etiologies of thrombosis include high fibrinogen and factor VIII levels, heparin resistance, and platelet activation. Achieving the optimal anticoagulation balance to prevent bleeding and thrombosis in ECMO patients is extremely complex. Experts in hemostasis should be a part of an institutional ECMO team and continuously available for immediate management.

Pre-existing risks to patients for hematologic events may be exacerbated by the ECMO. Blood exposure to artificial surfaces results in fibrinogen, albumin, and other proteins coating the artificial surface, platelet activation, and inflammation. This may be dampened by a heparin-bonded biomimetic surface which reduces cellular activation and inflammation, but systemic anticoagulation is still required.
 
The degree of thrombocytopenia is related to the patient's illness rather than the duration of ECMO treatment. The artificial cannulation surface and the shear stress may contribute to platelet activation and reduced platelet bonding, along with other factors, leading to thrombosis and bleeding.
 
Across multiple pediatric and adult studies, severe hemolysis occurs at a rate of 2-20%. Hemolysis is associated with increased rates of endothelial failure, kidney failure, thrombotic events, transfusions, and mortality.
 
Meta-analysis reports venovenous ECMO hemorrhage rates of 19% with pre-existing respiratory distress syndrome and central cannulation being 2 highly contributing factors.
 
All ECMO configurations carry high risk of infections between 13-40%.

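### The non-transfusion limb of the major hemolysis definition says *and* where *or* is almost certainly meant, so read literally no non-transfused survivor meets it

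*Protocol*

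**What the plan says.** Appendix 1 defines Amplifi System-related major hemolysis as hemolysis shown by laboratory testing during the treatment period, with no cause other than the device, that "requires blood transfusion and/or results in thrombotic events, multiple organ failure and mortality".

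Two operative parts of the protocol depend on this definition:

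- **Stop rule.** Under Section 7.2, when major hemolysis occurs during treatment, "the Investigator will discontinue Amplifi System treatment, provide treatment for the hemolysis, and create an AVF with the treated cephalic vein". The AVF step is to be prompt and applies only where the Subject's condition calls for it. The section adds that "Subject(s) will continue their post AVF follow-up, if applicable".
- **Safety composite.** Section 4.5 lists major hemolysis among the major device-related adverse events (MDRAE) and refers to the definitions attachment for detail. Device-related death is a separate component of the same composite.

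Neighbouring definitions in Appendix 1 list their consequences as alternatives. Major air embolism ends with "paradoxical embolization, myocardial infarction, stroke, mesenteric ischemia, or death". Major bleeding places "the administration of intravenous vasoactive agents for overt bleeding; or" before its last item, fatal bleeding. The major thrombosis and thromboembolism definitions expressly leave out a thrombectomy done during AVF creation.

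**The concern.** The *and/or* after transfusion makes transfusion sufficient on its own. The second limb is the difficulty. Its three consequences are joined by *and*, so on the literal text a non-transfused Subject must have a thrombotic event, multiple organ failure and death together.

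That limb cannot serve the purpose Section 7.2 gives it. Stopping the pump, treating the hemolysis, creating an AVF and continuing follow-up all presuppose a living Subject. Nor does the limb add to the composite, since a device-related death already counts there.

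At stake is whether stopping is mandatory or left to judgment for a non-transfused survivor whose pump is still running. A lesser question is whether such a Subject is counted under the hemolysis component.

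**Working it through.** The plan gives no figure to reproduce here: Section 14.1 says the study is not powered for a specific outcome. The check is one of logic, followed by a comparison of texts.

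**Inputs.** Four yes/no items from the Appendix 1 definition: transfusion (T), thrombotic event (Th), multiple organ failure (M), death (D). This gives 2^4 = 16 patterns.

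**Rules.**
- As written: T or (Th and M and D).
- With *or*: T or Th or M or D.

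**All patterns.** The 8 transfused patterns qualify under both rules. As written, one non-transfused pattern also qualifies: 8 + 1 = 9 of 16. With *or*, every non-transfused pattern with at least one consequence qualifies, 2^3 − 1 = 7, so 8 + 7 = 15 of 16. The rules differ in 15 − 9 = 6 patterns, all non-transfused.

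**The 7 non-transfused patterns.**

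| Pattern | *and* | *or* | Other route into the composite |
|---|---|---|---|
| Th | no | yes | major thrombosis or thromboembolism, if treated in a way those definitions count |
| M | no | yes | prolonged hospitalization, very likely |
| Th + M | no | yes | either of the above |
| D | no | yes | device-related death |
| Th + D | no | yes | device-related death |
| M + D | no | yes | device-related death |
| Th + M + D | yes | yes | device-related death |

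Survivors: 0 of 3 as written, 3 of 3 with *or*. Deaths: 1 of 4 as written, 4 of 4 with *or*, and all 4 count as device-related death in any case.

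**What is left for the count.** The main remaining case is Th alone, where the thrombus is cleared only by thrombectomy at AVF creation. Thrombolysis, long-term anticoagulation or a separate thrombectomy would bring the Subject in as major thrombosis or thromboembolism if imaging documents the event. With at most 10 Subjects, one reclassified Subject moves the hemolysis component by at least 1/10 = 10 percentage points. It moves the composite only if no other component applies.

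**What is left for the stop.** All 3 survivor patterns are mandatory stops under *or* and discretionary under *and*. This matters only while the pump is running; after a stoppage, Section 7.5 governs.

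**Which reading is meant.** The protocol's own text points to *or*:
- Section 7.2 assumes that the Subject survives.
- The air embolism and bleeding lists use *or*.
- Appendix 1 uses *and* loosely elsewhere. The thrombocytopenia definition has "not due to a cause other than the placement, operation, use, and removal of the Amplifi System, and requires transfusion", where the parallel definitions have *or* between use and removal. The list of maturation interventions joins alternatives with "remove thrombus from the lumen of the artery or vein in Study AVF circuit; and".
- Table 6 in Appendix 2 presents such consequences as separate outcomes: "Hemolysis is associated with increased rates of endothelial failure, kidney failure, thrombotic events, transfusions, and mortality".

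**The case against.** The strongest reply is that this is a copy-edit. The context just listed points to *or*, and an Investigator is unlikely to demand thrombosis, organ failure and death together before applying a rule that then orders an AVF. Section 7.2 sets a minimum and forbids no other stop. Section 6.2 allows discontinuation from the study for a serious adverse event or in the Subject's best interest, and Section 7.4 supports AVF creation at any time on the same ground. Treatment is inpatient, lasts at most 72 hours, and has daily blood count, PFH and LDH. Most affected cases reach the composite by another component or by the adjudicated catch-all, and Section 14.2.3 reports all adverse events by type. Leaving out thrombus cleared at AVF creation may be deliberate.

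Nearly all of this stands, and it keeps the point small. It does not remove it. Section 6.2 is permissive and concerns study participation, and Section 7.4 rests on judgment, whereas Section 7.2 is mandatory. It is the only hemolysis-specific mandatory stop in the protocol; the IFU is not at hand. A mandatory safety rule should not depend on readers correcting its trigger.

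A reader might infer that major hemolysis as a whole requires death, or that Appendix 1 and Section 7.2 contradict each other outright. Neither follows: transfusion alone meets the definition, and every step of Section 7.2 is then workable. The mismatch is confined to the non-transfusion limb.

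**Conclusion.** The point holds as a drafting slip in an operative safety definition. Read literally, 0 of the 3 non-transfused survivor patterns meet it, against 3 of 3 with *or*. The mandatory stop therefore misses these Subjects, and the limb adds nothing to the MDRAE composite beyond device-related death. Transfused Subjects are unaffected.

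The practical effect is small. That judgment assumes that organ failure would nearly always prolong hospitalization, that most thrombotic events would be treated in a way the thrombosis definitions count, and that Investigators would use their discretion to stop.

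A reader might go further and infer that the reported safety rate will be materially too low. The documents do not support that. The pattern counts carry no probabilities, and the protocol does not say what share of hemolysis would be non-transfused with a thrombotic event alone, so missed events cannot be computed. The hemolysis rates in Appendix 2 come from ECMO and do not measure how often this wording would matter.

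**What to change.** Reword the clause to: *requires blood transfusion, or results in a thrombotic event, multiple organ failure, or death*.

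Do not add a condition that the thrombotic event be documented by imaging. Routine daily ultrasound covers only the mid-forearm cephalic vein (Section 8.1.2), venography during treatment is required only after prolonged pump stoppage (Section 8.5.3), and end-of-treatment venography comes too late to trigger a stop. An imaging condition could therefore delay the stop or call for extra imaging.

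State also whether a thrombotic event cleared only by thrombectomy at AVF creation counts as major hemolysis when hemolysis coexists. The thrombosis and thromboembolism definitions exclude that thrombectomy, so counting it here re-admits an event left out there. The sponsor should decide this explicitly.

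The cost is one reworded definition, with no new visit, test or Subject. The reported event rate may be slightly less favourable, and stopping becomes mandatory in a few more situations.
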